2. YOUR BELIEFS ABOUT CHILDREN'S TEETH AND DENTAL CARE

Parents have different beliefs about children's teeth and getting dental care. Please tell us how much you agree or disagree with the following statements by circling the number that best fits your response.

	Strongly Agree	Agree	Neutral	Disagree	Strongly Disagree
2a. Most children eventually develop dental cavities.	1	2	3	4	5
2b. Cavities in baby teeth don't matter since they fall out anyway.	1	2	3	4	5
2c. I don't know how to get my child to the dentist to have his/her cavities fixed.	1	2	3	4	5
2d. If I took my child to the dentist, it would not make any difference whether or not he/she developed cavities.	1	2	3	4	5
2e. I intend to take my child to the dentist at least once a year.	1	2	3	4	5
2f. I cannot make my child go to the dentist.	1	2	3	4	5
2g. The dentist is the best person to prevent cavities in my child.	1	2	3	4	5
2h. I don't know how to brush my child's teeth properly.	1	2	3	4	5
2i. If I helped my child brush every day, it would not make any difference whether or not he/she developed cavities.	1	2	3	4	5
2j. I intend to brush my child's teeth for him/her twice a day.	1	2	3	4	5
2k. I cannot make my child brush his/her teeth twice daily.	1	2	3	4	5

Study Site: _____ ID#: _____

Caregiver Questionnaire-Final Follow-up

3. TAKING YOUR CHILD TO THE DENTIST

3a.-3b. The following questions are about what others think about taking your child to the dentist for preventive care and dental treatments. Please tell us how you feel by circling the number that best fits your response.

People important to me ...	Strongly Disagree	Disagree	Neutral	Agree	Strongly Agree
3a1. think that I should take my child to the dentist at least once a year .	1	2	3	4	5
3a2. would approve if I were to take my child to the dentist at least once a year .	1	2	3	4	5
3a3. take their child to the dentist at least once a year .	1	2	3	4	5
<hr/>					
3b1. think that I should take my child to the dentist when a tooth problem is found.	1	2	3	4	5
3b2. would approve if I were to take my child to the dentist when a tooth problem is found.	1	2	3	4	5
3b3. take their child to the dentist when a tooth problem is found.	1	2	3	4	5

□

Study Site: _____ ID#: _____

Caregiver Questionnaire-Final Follow-up

3c. Sometimes parents delay their child's dental care when other things get in the way. How likely are you to take your child to the dentist when the following happen to you? *Please circle the number that best fits your response.*

How likely are you to take your child to the dentist when you are ...	Very Likely	Moderately Likely	Somewhat Likely	Not At All Likely
3c1. under a lot of stress	1	2	3	4
3c2. depressed	1	2	3	4
3c3. anxious	1	2	3	4
3c4. feeling like you do not have the time (too busy)	1	2	3	4
3c5. tired	1	2	3	4
3c6. worrying about other things in your life	1	2	3	4
3c7. bothered by your crying child	1	2	3	4
3c8. bothered because your child will not stay still for the dentist to examine him/her	1	2	3	4
3c9. told by your child that he/she does not feel like going to the dentist	1	2	3	4

Study Site: _____ ID#: _____

Caregiver Questionnaire-Final Follow-up

4. YOUR CHILD'S ORAL HEALTH BEHAVIOR

Please circle the letter of the response that best fits your child.

4.1 During an ideal week, how often does your child brush his/her teeth?

- a) Doesn't brush his/herteeth
- b) Less than once a week
- c) Once or twice a week
- d) About every other day
- e) Almost every day
- f) Once a day
- g) Twice a day
- h) More than twice a day
- i) Don't know

4.2 Since the start of this school year, did your child have any kind of dental coverage, such as a private plan, preferred plan (like an HMO), or government plan (like Medicaid)?

- a) Yes → Please answer Question 4.2a
- b) No
- c) Don't know

4.2a Was your child insured by Medicaid or the State Children's Health Insurance Program (S-CHIP)?

- a) Yes
- b) No
- c) Don't know

4.3 Is there a place your child usually goes when he/she needs treatment for a dental problem, like a cavity or tooth pain?

- a) Yes → Please answer Question 4.3a
- b) No
- c) Don't know

Study Site: _____ ID#: _____

Caregiver Questionnaire-Final Follow-up

4.3a If you answered YES, is this place a:

- a) Dentist's office
- b) Emergency department
- c) Hospital
- d) Clinic
- e) Other, please specify _____

4.4 Sometimes people have trouble getting all the dental treatment they need. Since the start of this school year, was there any time when your child needed dental care but it was delayed or not received?

- a) Yes → Please answer Question 4.4a
- b) No
- c) Don't know } Please skip to Question 4.5

4.4a What type of treatment was delayed or not received after a problem had been found by a dental provider? Please circle all that apply.

- a) Filling
- b) Extraction [having a tooth pulled]
- c) Crown / metal cap
- d) Pulp therapy [baby root canal]
- e) Gum disease
- f) Other, please specify _____
- g) Don't remember

4.5 Did your child visit the dentist after the school dental screening?

- a) Yes → Go to Question 5A
- b) No → Go to Question 5B

Study Site: _____ ID#: _____

Caregiver Questionnaire-Final Follow-up

5A. YOUR THOUGHTS ABOUT THE STUDY

If you answered YES to Question 4.5 (your child visited the dentist), please answer the following questions:

5.1. What is the name of the dental clinic / dentist where you took your child?

5.2. What month after the dental screening did you take your child to the dentist?

5.3. Did you take the referral letter (from the school dental screening) with you to the dentist?

- a) Yes
- b) No

5.4. Did your child complete the needed dental treatment?

- a) Yes

If YES, how many visits were needed to complete your child's dental treatment? _____

- b) No, but my child has a follow-up appointment

If NO, when is the follow-up appointment? _____

- c) No

If NO, why did your child not complete dental treatment? _____

- d) Don't know

Please GO TO Question 5.5

Study Site: _____ ID#: _____

Caregiver Questionnaire-Final Follow-up

5.5 Were there any items below that helped you get your child to the dentist?*Please circle all that apply.*

- a) The referral letter
- b) Information on myths and facts of children's dental health
- c) Helpful hints on getting my child dental care
- d) Information on making a dental appointment for my child
- e) Knowing about the dentists in my area
- f) The outreach individual at my child's school
- g) Don't know

5.6 Did you find the referral letter easy to understand?

- a) Yes
- b) No

5.7 Which study group do you think you and your child were in?

- a) Standard letter
- b) Improved letter
- c) Improved letter with materials
- d) Don't know

THANK YOU!

Study Site: _____ ID#: _____

Caregiver Questionnaire-Final Follow-up

5B. YOUR THOUGHTS ABOUT THE STUDY

*If you answered **NO** to Question 4.5 (your child did not visit the dentist), please answer the following questions:*

5.1. The following questions are about taking your child to the dentist. Please circle the number that best fits your response.

	Strongly Disagree	Disagree	Neither disagree nor agree	Agree	Strongly Agree
5.1a I want to take my child to the dentist.	1	2	3	4	5
5.1b I plan to take my child to the dentist.	1	2	3	4	5

5.2. Why has your child NOT been able to visit the dentist since the school dental screening? Here are some common reasons from other parents — please circle all that apply.

- a) The cost is too much.
- b) My child does not have dental insurance or Medicaid.
- c) My family has a problem with our health care plan.
- d) I cannot find a dentist who accepts my child's insurance.
- e) There are no available dentists in my area / I have transportation problems.
- f) It is difficult to get convenient appointment times / My child could not get an appointment.
- g) The dentist did not know how to treat or provide care for my child.
- h) I was dissatisfied with the dentist.
- i) I did not know where to take my child for treatment.
- j) My child refused to go.
- k) My child's treatment is ongoing.
- l) Other, please specify _____

Study Site: _____ ID#: _____

Caregiver Questionnaire-Final Follow-up

5.3 Were there any items below that would have helped you get your child to the dentist?*Please circle all that apply.*

- a) The referral letter
- b) Information on myths and facts of children's dental health
- c) Helpful hints on getting my child dental care
- d) Information on making a dental appointment for my child
- e) Knowing about the dentists in my area
- f) The outreach individual at my child's school
- g) Don't know

5.4 Did you find the referral letter easy to understand?

- a) Yes
- b) No

5.5 Which study group do you think you and your child were in?

- c) Standard letter
- d) Improved letter
- e) Improved letter with materials
- f) Don't know

THANK YOU!

Site: _____ ID# _____

Estudio de Acceso de la Familia al Dentista

**Sus Sentimientos
Acerca de la Caries**

29 de Enero de 2015

**Punto de
Referencia IPQ-RD**

Site: _____ ID# _____

Instrucciones:

Nosotros estamos interesados en su punto de vista acerca de las caries en su niño/a (caries en el diente). Por favor indique cuanto usted está de acuerdo o desacuerdo con las siguientes oraciones acerca de la caries al hacer un círculo en las siguientes respuestas de cada pregunta: *totalmente de acuerdo (1), de acuerdo (2), ni de acuerdo ni en desacuerdo (3), desacuerdo (4), en total desacuerdo (5)*.

Por favor diganos si cree que cada una de las siguientes es un síntoma relacionado a caries dentales en los niños/as:

1a.	Dolor de diente	Yes	No
1b.	Dientes sensibles a lo caliente o helado	Yes	No
1c.	Hoyo en el diente	Yes	No
1d.	Manchas blancas o oscuras en los dientes	Yes	No
1e.	Inflamación en la cara o encillas (incluyendo una postemilla o absceso)	Yes	No

Por favor haga un círculo en el número de la mejor respuesta para cada pregunta. Si su niño/a no ha tenido caries, por favor responda como se sentiría si ellos tuvieran.

Acerca de su niño/a:	Totalmente de acuerdo	De acuerdo	Ni de acuerdo ni en desacuerdo	Desacuerdo	En total desacuerdo
2. Las caries en mi niño/a es una enfermedad seria.	1	2	3	4	5
3. Las caries en mi niño/a han tenido un gran efecto en su vida.	1	2	3	4	5
4. Las caries en mi niño/a han tenido un gran efecto en como el/ella sonríe.	1	2	3	4	5
5. Las caries en mi niño/a han tenido un gran efecto en como el/ella se comporta en la casa.	1	2	3	4	5
6. Las caries en mi niño/a han tenido un gran efecto en como hace el/ella su trabajo en la escuela.	1	2	3	4	5
7. Las caries en mi niño/a han tenido un gran efecto en como se siente acerca de el/ella misma.	1	2	3	4	5
8. Las caries en mi niño/a es una incapacidad.	1	2	3	4	5

Site: _____ ID# _____

Acerca de usted:	Totalmente de acuerdo	De acuerdo	Ni de acuerdo ni en desacuerdo	Desacuerdo	En total desacuerdo
9. Las caries en mi niño/a tienen un gran impacto en mi vida.	1	2	3	4	5
10. Simplemente no puedo vivir con las caries de mi niño/a.	1	2	3	4	5
11. Las caries en mi niño/a tienen un gran efecto en como otros me ven.	1	2	3	4	5
12. Las caries en mi niño/a me ha causado problemas de dinero.	1	2	3	4	5
13. Las caries en mi niño/a tienen un gran efecto en mi autoestima.	1	2	3	4	5

Acerca de su niño/a:	Totalmente de acuerdo	De acuerdo	Ni de acuerdo ni en desacuerdo	Desacuerdo	En total desacuerdo
14. Hay mucho que se puede hacer para mejorar las caries en mi niño/a.	1	2	3	4	5
15. El tratamiento en mi niño/a le ayudara a mejorar sus caries.	1	2	3	4	5
16. El mejoramiento en las caries de su niño/a no va a cambiar por casualidad o destino.	1	2	3	4	5
17. Lo que haga mi niño/a decidirá si sus caries mejoran o empeoran.	1	2	3	4	5

Acerca de usted:	Totalmente de acuerdo	De acuerdo	Ni de acuerdo ni en desacuerdo	Desacuerdo	En total desacuerdo
18. Hay mucho que yo puedo hacer para controlar los síntomas de la caries de mi niño/a.	1	2	3	4	5
19. Lo que yo haga decide si las caries mi niño/a se mejoran o empeoran.	1	2	3	4	5
20. Es mucho lo que yo puedo hacer para parar las caries de mi niño/a una vez que empiezan.	1	2	3	4	5
21. Es mucho lo que yo puedo hacer para prevenir las caries en mi niño/a.	1	2	3	4	5

Site: _____ ID# _____

Acerca de su niño/a:

	Totalmente de acuerdo	De acuerdo	Ni de acuerdo ni en desacuerdo	Desacuerdo	En total desacuerdo
--	-----------------------	------------	--------------------------------	------------	---------------------

22. Las caries de mi niño/a no se mejorarán con el tiempo.

1	2	3	4	5
---	---	---	---	---

23. Es probable que las caries en mi niño/a sean duraderas y no a corto plazo.

1	2	3	4	5
---	---	---	---	---

Acerca de su niño/a:

	Totalmente de acuerdo	De acuerdo	Ni de acuerdo ni en desacuerdo	Desacuerdo	En total desacuerdo
--	-----------------------	------------	--------------------------------	------------	---------------------

24. Las caries en mi niño/a podrían cambiar de vez en cuando.

1	2	3	4	5
---	---	---	---	---

25. Habrá momentos cuando los síntomas de las caries de mi niño/a se empeoran y tiempos cuando se mejoran.

1	2	3	4	5
---	---	---	---	---

Acerca de usted:

	Totalmente de acuerdo	De acuerdo	Ni de acuerdo ni en desacuerdo	Desacuerdo	En total desacuerdo
--	-----------------------	------------	--------------------------------	------------	---------------------

26. Tengo un claro entendimiento de las caries de mi niño/a.

1	2	3	4	5
---	---	---	---	---

27. Los síntomas de las caries de mi niño/a no son confuso para mí.

1	2	3	4	5
---	---	---	---	---

Acerca de usted:

	Totalmente de acuerdo	De acuerdo	Ni de acuerdo ni en desacuerdo	Desacuerdo	En total desacuerdo
--	-----------------------	------------	--------------------------------	------------	---------------------

28. Me pongo muy triste y molesto cuando pienso que mi niño/a está sufriendo de caries.

1	2	3	4	5
---	---	---	---	---

29. Ver a mi niño/a con caries me preocupa.

1	2	3	4	5
---	---	---	---	---

30. Ver a mi niño/a con caries me hace sentir enojado.

1	2	3	4	5
---	---	---	---	---

31. Ver a mi niño/a con caries me hace sentir impotente.

1	2	3	4	5
---	---	---	---	---

Site: _____ ID# _____

32. Causas de las caries en los niños/as:

Nosotros estamos interesados en su punto de vista acerca de las caries de su niño/a. No hay una respuesta correcta. Nosotros estamos interesados en sus propias ideas acerca de las causas de las caries de su niño/a en lugar de lo que otros (incluyendo doctores o familia) puedan haberle dicho. Abajo esta una lista de posibles causas.

Por favor Indique cuanto usted está de acuerdo o desacuerdo con cada causa haciendo un círculo al número que mejor se adapte a su respuesta: *totalmente de acuerdo (1), de acuerdo (2), ni de acuerdo ni de desacuerdo (3), desacuerdo (4), totalmente en desacuerdo (5)*.

Por favor haga un círculo en el número de la mejor respuesta

	Totalmente de acuerdo	De acuerdo	Ni de acuerdo ni en desacuerdo	Desacuerdo	En total desacuerdo
32a. La causa de la caries en mi niño/a es el estrés o preocupación.	1	2	3	4	5
32b. La caries corren en mi familia.	1	2	3	4	5
32c. Un germen o virus causó la caries de mi niño/a.	1	2	3	4	5
32d. La dieta o hábitos alimenticios causaron la caries en mi niño/a.	1	2	3	4	5
32e. Casualidad o suerte causaron las caries de mi niño/a.	1	2	3	4	5
32f. El pobre cuidado dental causó la caries de mi niño/a.	1	2	3	4	5
32g. Algo que yo hice como padre/madre causó la caries a mi niño/a.	1	2	3	4	5
32h. Mis pensamientos negativos causaron la caries de mi niño/a.	1	2	3	4	5
32i. Los problemas de familia o preocupaciones causaron la caries en mi niño/a.	1	2	3	4	5
32j. Mis sentimientos (sentime decaído, ansioso) le causó la caries a mi niño/a.	1	2	3	4	5
32k. La falta de habilidad de pelear la infección causó la caries de mi niño/a.	1	2	3	4	5

Site: _____ ID# _____

33. Por favor escriba en orden las 3 cosas más importantes que usted cree ahora causaron la caries de su niño/a. Usted puede usar cualquiera de los artículos de las preguntas anteriores o que tenga otras ideas propias.

Las causas más importantes para mí son:

1st _____

2nd _____

3rd _____

sitio del estudio _____ # de identificación _____

Cuestionario del cuidador -Referencia

Estudio de Acceso de la Familia al Dentista

**Cuestionario del
Cuidador**

29 de Junio, 2015

Punto de Referencia

sitio del estudio _____ # de identificación _____

Cuestionario del cuidador -Referencia

Fecha de la entrevista _____
Mes día año

Iniciales del entrevistador _____

1. INFORMACIÓN DE ANTECEDENTES**1.1 Su edad** _____ años**1.2 Su raza y etnicidad (origen étnico)****1.2a Su raza****1.2b Su etnicidad**

Por favor marque con una X todas las que apliquen Por favor marque solo una con una X

Blanco _____

No Hispano /Latino _____

Asiático _____

Hispano/ Latino _____

Indio Americano / Nativo de Alaska _____

Desconocido _____

Hawaiano (Nativo de las islas del
Pacifico) _____

Más de una raza _____

Desconocido _____

1.3 Su estado marital

Por favor marque solo uno con una X

Casado _____

Soltero _____

Derecho común _____

Divorciado _____

Separado _____

Viudo _____

Desconocido _____

sitio del estudio _____ # de identificación _____

Cuestionario del cuidador -Referencia

1.4 ¿Si usted es el padre o la madre, ¿está el otro parente o madre viviendo con usted?

Si _____

No _____

1.5 Su educación**1.5a. Su más alto nivel de educación completo. Por favor, marque solo uno con una X**

Título de posgrado _____

Algunos años de educación superior _____

Título de Universidad/Colegio _____

Algunos estudios de Universidad _____

Diploma de bachillerato /
examen de desarrollo de educación general
(GED por sus siglas en Ingles) _____

Grados 10 – 11 _____

Grados 7 – 9 _____

Grados 1 – 6 _____

Desconocidos _____

1.5b ¿Cuantos años de escuela ha completado? _____ años**1.6 ¿Cual es su (sus) ocupación (es) actual? Por favor escriba su respuesta (s) abajo:**

sitio del estudio _____ # de identificación _____

Cuestionario del cuidador -Referencia

2. SUS CREENCIAS ACERCA DE LOS DIENTES DE LOS NIÑOS Y EL CUIDADO DENTAL

Los padres tienen diferentes creencias acerca de los dientes de los niños/as y obtener el cuidado dental. *Por favor diganos cuanto está usted de acuerdo o desacuerdo con las siguientes declaraciones al circular el número que mejor se ajuste a su respuesta.*

	Totalmente de acuerdo	De acuerdo	Ni de acuerdo ni en desacuerdo	Desacuerdo	En total desacuerdo
2a. Eventualmente la mayoría de los niños/as desarrollan caries dentales	1	2	3	4	5
2b. Las caries en los dientes de leche no importan ya que de todos modos se caen	1	2	3	4	5
2c. No sé cómo llevar a mi niño/a al dentista para que le arreglen sus caries.	1	2	3	4	5
2d. Si me llevé a mi hijo al dentista, no haría ninguna diferencia si o no él/ella desarrolle caries.	1	2	3	4	5
2e. Yo intentaré llevar a mi niño/a al dentista al menos una vez al año.	1	2	3	4	5
2f. No puedo hacer que mi niño/a vaya al dentista.	1	2	3	4	5
2g. El dentista es la mejor persona para prevenir las caries de mi niño/a.	1	2	3	4	5
2h. No sé cómo cepillarle los dientes apropiadamente a mi niño/a.	1	2	3	4	5
2i. Si le ayudo a mi niño/a cepillarse todos los días, no hará ninguna diferencia si o no él/ella desarrolle caries	1	2	3	4	5
2j. Intento cepillarle los dientes a mi niño/a dos veces al día.	1	2	3	4	5
2k. No puedo hacer que mi niño/a cepille sus dientes dos veces al día.	1	2	3	4	5

sitio del estudio _____ # de identificación _____

Cuestionario del cuidador -Referencia

3. SUS PENSAMIENTOS ACERCA DE VISITAR AL DENTISTA

Las siguientes preguntas son acerca de cómo usted se siente en el dentista. Díganos cuan ansioso usted se sentiría en las siguientes situaciones *haciendo un círculo al número que mejor se adapte a su respuesta.*

Como se sentiría usted si...	Extremadamente ansioso	Muy ansioso	Bastante ansioso	Ligeramente ansioso	Nada ansioso
3a. Va a ir al dentista MANANA para TRATAMIENTO?	1	2	3	4	5
3b. ¿Está sentado en la SALA DE ESPERA (esperando por tratamiento)?	1	2	3	4	5
3c. ¿Está a punto de que le PERFOREN UN DIENTE?	1	2	3	4	5
3d. ¿Está a punto de tener sus dientes ESCALADOS y PULIDOS?	1	2	3	4	5
3e. ¿Está a punto de ponerle una INYECCIÓN de ANESTESIA LOCAL en sus encillas?	1	2	3	4	5

4. SUS PENSAMIENTOS ACERCA DE LLEVAR A SU NIÑO/A AL DENTISTA

4a. Las siguientes preguntas son acerca de llevar a su niño/a al dentista por cualquier razón. *Por favor circule el número que mejor se adapte a su respuesta.*

	Completamente en desacuerdo	Desacuerdo	Neutral	De acuerdo	Totalmente de acuerdo
4a1. Yo quiero llevar a mi niño al dentista	1	2	3	4	5
4a2. Yo planeo llevar a mi niño al dentista	1	2	3	4	5

sitio del estudio _____ # de identificación _____

Cuestionario del cuidador -Referencia

4b. Las siguientes preguntas son acerca de cómo usted se siente acerca de llevar a su niño/a al dentista para cuidado preventivo (chequeos, limpiezas, aplicación de fluoruro) y tratamientos dentales (arreglar caries) Y lo que otros piensan acerca de llevar a su niño/a al dentista para cuidado preventivo y de tratamiento dental. *Díganos como se siente, al hacer un círculo en el número que mejor se adapte a su respuesta.*

Mi sentimiento acerca del dentista es que se atraviesa en el camino si llevo a mi niño/a al dentista para ...	Completa- mente en desacuerdo	Desacuerdo	Neutral	De acuerdo	Totalmente de acuerdo
	1	2	3	4	5
4b1. Cuidado Preventivo					
4b2. Tratamiento Dental					

4c. – 4d.

Personas importantes para mí ...	Completa- mente en desacuerdo	Desacuerdo	Neutral	De acuerdo	Totalmente de acuerdo
	1	2	3	4	5
4c1. Piensan que debería llevar a mi niño/a al dentista dos veces al año					
4c2. Aprobarían si tuviera que llevar a mi niño/a al dentista dos veces al año					
4c3. Llevan a su niño dos veces al año					
4d1. Piensan que cuando se encuentre un problema en un diente debería llevar a mi niño/a al dentista					
4d2. Aprobarían que llevara a mi niño/a al dentista cuando se encuentre un problema en el diente					
4d3. Llevan a su niño/a al dentista cuando se encuentre un problema en un diente					

sitio del estudio _____ # de identificación _____

Cuestionario del cuidador -Referencia

4e. Algunas veces los padres atrasan el cuidado dental de su niño/a cuando otras cosas se presentan en el camino. ¿Qué probabilidades hay que lleve a su niño/a al dentista cuando lo siguiente le pase? Por favor circule el número que mejor se adopte a su respuesta.

Que probabilidades hay que usted lleve a su niño/a al dentista cuando usted está ...	Muy Probable	Moderadamente probablemente	Possiblemente	No hay probabilidad
4e1. Bajo mucho estrés	1	2	3	4
4e2. Deprimida	1	2	3	4
4e3. Ansiosa	1	2	3	4
4e4. Sintiéndose que no tiene el tiempo (muy ocupado)	1	2	3	4
4e5. Cansada	1	2	3	4
4e6. Preocupada por otras cosas en su vida	1	2	3	4
4e7. Molesta por su niño/a llorando	1	2	3	4
4e8. Molesta porque su niño/a no se está quieto para que el dentista lo examine	1	2	3	4
4e9. Su niño/a le dijo que no quiere ir al dentista	1	2	3	4

sitio del estudio _____ # de identificación _____

Cuestionario del cuidador -Referencia

5. Sus sentimientos y pensamientos durante el último mes

Para cada pregunta siguiente, *por favor circule cuan frecuente sintió o pensó de esa manera en el último mes.*

	Muy amenudo	Bastante amenudo	Algunas veces	Casi nunca	Nunca
5a. ¿En el último mes, con que frecuencia se ha sentido que no ha podido controlar las cosas importantes en su vida?	0	1	2	3	4
5b. ¿En el último mes, con que frecuencia se ha sentido confiado acerca de sus habilidades de manejar sus problemas personales?	0	1	2	3	4
5c. ¿En el último mes, que frecuencia se ha sentido que las cosas iban a su manera?	0	1	2	3	4
5d. ¿En el último mes, con que frecuencia se ha sentido que las dificultades se acumulan tan alto que no podía solucionarlas?	0	1	2	3	4

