Confounders	Child's age, race, dental visit Caregiver socio-demographics (age, race, SES, education, marital status)	Baseline	NHANES IV
Subject compliance with Intervention	
 • Whether the referral letter (and DIG) was received (generic code) • Whether the referral letter (and DIG) was read/understood (Postcard) 	Within 2 days after Baseline dental exam	

1. **Baseline:** prior to screening dental exam; **At randomization:** after baseline dental screening exam; **Two-weeks:** Two weeks after randomization; **Exit:** two weeks before end of school year dental exam

2. Caregiver self-efficacy and subjective norms will also be considered as potential **mediators** in the additional mediational analyses, and will be measured at the **Exit** in addition to **Baseline**.

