4. TAKING YOUR CHILD TO THE DENTIST

4a. The following questions are about taking your child to the dentist for any reason. Please circle the number that best fits your response.

	Strongly Disagree	Disagree	Neither disagree nor agree	Agree	Strongly Agree
4a1. I want to take my child to the dentist.	1	2	3	4	5
4a2. I plan to take my child to the dentist.	1	2	3	4	5

Study Site _____ ID# _____

Caregiver Questionnaire-Baseline

4b. The following questions are about how you would feel about taking your child to the dentist for preventive care (checkups, cleanings, topical fluoride) and dental treatments (fixing cavities). Please tell us how you feel by circling the number that best fits your response.

My feelings about the dentist will get in the way of taking my child to the dentist for...	Strongly Disagree	Disagree	Neutral	Agree	Strongly Agree
4b1. preventive care.	1	2	3	4	5
4b2. dental treatments.	1	2	3	4	5

4c.– 4d. The following questions are about what others think about taking your child to the dentist for preventive care and dental treatments. Please tell us how you feel by circling the number that best fits your response.

People important to me ...	Strongly Disagree	Disagree	Neutral	Agree	Strongly Agree
4c1. think that I should take my child to the dentist at least once a year.	1	2	3	4	5
4c2. would approve if I were to take my child to the dentist at least once a year.	1	2	3	4	5
4c3. take their child to the dentist at least once a year.	1	2	3	4	5
4d1. think that I should take my child to the dentist when a tooth problem is found.	1	2	3	4	5
4d2. would approve if I were to take my child to the dentist when a tooth problem is found.	1	2	3	4	5
4d3. take their child to the dentist when a tooth problem is found.	1	2	3	4	5

Study Site _____ ID# _____

Caregiver Questionnaire-Baseline

4e. Sometimes parents delay their child's dental care when other things get in the way. How likely are you to take your child to the dentist when the following happen to you? Please circle the number that best fits your response.

How likely are you to take your child to the dentist when you are ...	Very Likely	Moderately Likely	Somewhat Likely	Not At All Likely
4e1. under a lot of stress	1	2	3	4
4e2. depressed	1	2	3	4
4e3. anxious	1	2	3	4
4e4. feeling like you do not have the time (too busy)	1	2	3	4
4e5. tired	1	2	3	4
4e6. worrying about other things in your life	1	2	3	4

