3. SUS PENSAMIENTOS ACERCA DE LLEVAR A SU NIÑO/A AL DENTISTA

3a – 3b. Las siguientes preguntas son acerca de lo que otros piensan acerca de llevar a su niño/a al dentista para cuidado preventivo y tratamiento dental. *Por favor diganos como se siente haciendo un círculo en el número que se ajuste a su respuesta.*

Personas importantes para mí ...	Completamente en desacuerdo	Desacuerdo	Neutral	De acuerdo	Totalmente de acuerdo
3a1. Piensan que debería llevar a mi niño/a al menos una vez al año.	1	2	3	4	5
3a2. Aprobarían si tuviera que llevar a mi niño/a al dentista al menos una vez al año.	1	2	3	4	5
3a3. Llevan a su niño/a al dentista al menos una vez al año.	1	2	3	4	5
<hr/>					
3b1. Piensan que cuando se encuentre un problema en un diente debería llevar a mi niño/a al dentista	1	2	3	4	5
3b2. Aprobarían que llevara a mi niño/a al dentista cuando se encuentre un problema en el diente	1	2	3	4	5
3b3. Llevan a su niño/a al dentista cuando se encuentre un problema en un diente	1	2	3	4	5

Sitio del estudio: _____ # de identificación: _____

Cuestionario del cuidador Ultimo seguimiento

3c. Algunas veces los padres atrasan el cuidado dental de su niño/a cuando otras cosas se presentan en el camino. ¿Qué probabilidades hay que lleve a su niño/a al dentista cuando lo siguiente pase? Por favor circule el número que mejor se adapte a su respuesta.

Que probabilidades hay que usted lleve a su niño/a al dentista cuando usted está ...	Muy Probable	Moderadamente probablemente	Possiblemente	No hay probabilidad
3c1. Bajo mucho estrés	1	2	3	4
3c2. Deprimida	1	2	3	4
3c3. Ansiosa	1	2	3	4
3c4. Sintiéndose que no tiene el tiempo (muy ocupado)	1	2	3	4
3c5. Cansada	1	2	3	4
3c6. Preocupada por otras cosas en su vida	1	2	3	4
3c7. Molesta por su niño/a llorando	1	2	3	4
3c8. Molesta porque su niño/a no se está quieto para que el dentista lo examine	1	2	3	4
3c9. Su niño/a le dijo que no quiere ir al dentista	1	2	3	4

Sitio del estudio: _____ # de identificación: _____

Cuestionario del cuidador Último seguimiento

4. EL COMPORTAMIENTO DEL CUIDADO DENTAL DE SU NIÑO/A*Por favor haga un círculo en la letra que mejor se adapte a su respuesta acerca de su niño/a.***4.1 Durante una semana *ideal*, ¿cuán frecuente se cepilla los dientes su niño/a?**

- a) No se cepilla sus dientes
- b) Menos de una vez a la semana
- c) Una o dos veces a la semana
- d) Un día si un día no
- e) Casi todos los días
- f) Una vez al día
- g) Dos veces al día
- h) Mas de 2 veces al día

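### Three of six subjective-norm items on the Spanish baseline form ask about a different visit frequency from the other three forms, so the score is not comparable for Spanish-form caregivers

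*Combined protocol and SAP*

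**What the plan says.** Appendix C contains four forms that carry the six items introduced by the stem about people important to the caregiver: baseline and exit, each in English and Spanish.

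- Spanish baseline (section 4), item 4c1: "Piensan que debería llevar a mi niño/a al dentista dos veces al año". Items 4c2 (whether those people would approve) and 4c3 (what they do with their own child) use the same frequency.
- English baseline (section 4), item 4c1: "think that I should take my child to the dentist at least once a year". Items 4c2 and 4c3 use the same frequency, as do English exit items 3a1–3a3.
- Spanish exit (section 3), item 3a1: "Piensan que debería llevar a mi niño/a al menos una vez al año". Items 3a2 and 3a3 use the same frequency.

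The other three items concern taking the child when a dental problem has been found and carry no frequency. On the Spanish baseline form the first of them reads "4d1. Piensan que cuando se encuentre un problema en un diente debería llevar a mi niño/a al dentista".

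Table 3.2.1 lists subjective norm among the moderators, measured at baseline. Footnote 2 adds "Caregiver self-efficacy and subjective norms will also be considered as potential" mediators, measured at exit as well as baseline. Sections 4.2 and 6.1 give the reason: the letter text may also map to the Theory of Planned Behavior, and subjective norms are one way to examine that rival explanation.

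**The concern.** A caregiver who uses the Spanish forms is asked about two visits a year in October and at least one in the spring. Part of any baseline-to-exit difference on those items may then reflect the question rather than the norm. At baseline, the Spanish and English answers to the same three item numbers are answers to different questions.

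Two exploratory uses are exposed. In a moderator analysis, a baseline score containing 4c1–4c3 partly marks which language form was filled in, so an arm-by-norm interaction could pick up an arm-by-language difference. In a mediation analysis using baseline and exit, the association between norm and receipt of dental care could be confounded by language, and by whatever goes with language in these communities.

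**Working it through.** No sample size, power or alpha figure is involved, and the plan states no figure to reproduce. The check is a word-by-word comparison of the six items on the four forms.

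| Form | First three items | Frequency asked | Other three items | Content |
|---|---|---|---|---|
| English baseline | 4c1–4c3 | at least once a year | 4d1–4d3 | once a tooth problem is found |
| English exit | 3a1–3a3 | at least once a year | 3b1–3b3 | same |
| Spanish baseline | 4c1–4c3 | **twice a year** | 4d1–4d3 | same |
| Spanish exit | 3a1–3a3 | at least once a year | 3b1–3b3 | same |

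Counts from the table:

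- Over time, the frequency changes for 3 of 6 items in Spanish and 0 of 6 in English.
- Between languages, it differs for 3 of 6 items at baseline and 0 of 6 at exit.

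**Is it a reading error or an old version?** No. The phrase occurs in three separate items. Item 2e of the same Spanish form gives the frequency as at least once a year. All four forms carry the same date, 29 June 2015. The intervention letter (Table 6.1.1, controllability) also speaks of at least one visit a year, so the Spanish baseline items depart from the message being tested as well. Section 6.1 describes back-translation for the letters; the supplied text describes none for the questionnaires.

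**A smaller slip.** Spanish baseline 4c3 does not mention the dentist, although its exit counterpart 3a3 does.

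**Which way would the wording push?** For 4c1 and 4c3, twice a year is the stricter standard: it implies at least once, and the reverse does not hold. Agreement could therefore rise by exit with no change in norms. For 4c2 (approval) the wording does not settle the direction, since people may approve of two visits as readily as of one.

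**How large could it be?** Two inputs are missing: the share of caregivers on Spanish forms and the scoring rule. As an illustration only, assume that the score is the mean of six items and that the wording moves each affected item by *d* points on the 1–5 scale. The artefact for a Spanish-form caregiver is then (3/6) × *d*. With an assumed *d* of 0.3 it is 0.5 × 0.3 = 0.15 points; with 0.8 it is 0.5 × 0.8 = 0.40 points. Neither the scoring nor the range of *d* comes from the documents.

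**Where does it enter a mediation analysis?** Section 4.2 has the baseline forms completed before randomization, and Section 5.4.1 stratifies randomization by grade and school. The artefact therefore has the same expectation in every arm. Exit wording agrees across languages, so an arm comparison of the exit score is unaffected. What remains exposed is the norm-to-care link. The adjustment covariates in Section 12.4 are child's age, race, caregiver SES, education and marital status, plus site in the overall model. Form language is not among them, and site cannot separate Spanish-form from English-form families within Washington.

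**The case against.** The strongest reply is that little in the plan rests on this score. Section 3.2.2 defines change scores only for IPQ-RD and behavioral intention. The one alternative-theory analysis spelled out in Section 12.4 uses self-efficacy, and that section describes no moderator model. The running text of Section 4.2 omits subjective norm from its list of moderators, so that role rests on Table 3.2.1. As a mediator the construct is only to be considered. This stands, and it makes the point one about exploratory work.

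Reach may also be small. The Protocol Summary places the Hispanic families in Washington, and the second recruitment year in Section 5.3 is confined to Ohio districts, so a corrected form may come too late for most Spanish-form families. That is a fair limit on the value of correcting the form. It does not help with forms already collected.

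Site and race in the model may absorb part of a language effect. They do so only in part, for the reason given in the check.

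A reader might go further and infer that the test of the rival theory becomes uninterpretable, or that the comparison of arms is biased. The documents do not support either. Half the items match on all four forms, the exit wording matches throughout, and the fault precedes randomization. Nor do they support dropping the three frequency items for everyone: English-form answers to them are consistent at both times, and discarding them from the main score is a debatable trade.

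**Conclusion.** The mismatch is certain and its consequence is limited. Any subjective-norm score that includes 4c1–4c3 lacks a common meaning across languages at baseline and across time in Spanish. That can bias the exploratory moderator and mediator uses, mainly through the norm-to-care association.

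No numerical size can be attached. The 0.15 to 0.40 point illustration should not be read as an estimate: it depends on an assumed six-item mean and an assumed wording effect, and the direction is open for 4c2.

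The conclusion rests on one inference. The questionnaires do not label these items as subjective norm, but the stem leaves no other plausible reading. The supplied text gives no scoring rule. The Manual of Procedures and a separate SAP are listed as supplemental materials and may contain one.

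**What to change.** 1. For any further use, give Spanish baseline items 4c1–4c3 the frequency phrase of the Spanish exit items (*al menos una vez al año*), and add *al dentista* to 4c3.
2. For Spanish baseline forms already collected, treat 4c1–4c3 as not equivalent, so that they enter no pooled baseline score and no baseline-to-exit change.
3. State the subjective-norm scoring rule, and report the moderator and mediator analyses with a score built only from 4d1–4d3 at baseline and 3b1–3b3 at exit, at least as a sensitivity analysis.

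After step 2 a full six-item baseline score exists only for English forms and any corrected Spanish forms. Averaging the remaining three items for the other Spanish-form caregivers against six for everyone else would mix item content again, which is why step 3 uses the same three items for all.

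The cost is one corrected form and a few sentences on scoring. The downside is a three-item instead of a six-item scale in that analysis.
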